**Impact of a Virtual Diabetes Self-Care and Education Program
on Diabetes-related Outcomes in Latinos with T2 Diabetes**

NCT02488785

Document date Oct 27/2015

PROGRAM DESCRIPTION/PLAN OF OPERATION

PURPOSE OF PROTOCOL:

The goal of this study is to evaluate the impact of a comprehensive diabetes education and management program based on frequent communication with patients using teleconsultation, text messaging, and phone calls on diabetes related outcomes in Latino patients with type 2 diabetes. We hypothesize that the decline in hemoglobin A1c value between the baseline and the six-month visit will be at least 0.5 percent greater in the intervention group than in the control group.

1. Objectives:

- a. Improve adherence to nutritional therapy, physical activity, glucose monitoring and medication use in Latino patients with type 2 diabetes by using a virtual diabetes education and self-management program in a six month period and in comparison to usual diabetes care and education received in diabetes clinics.
- b. Improve A1c levels, blood pressure, lipids and weight control in Latino patients with diabetes using this program within the same time frame.
- c. Improve adherence to clinic appointments and decrease diabetes related stress, depression, visits to the emergency room and hospitalizations with the use of this program in comparison to people receiving usual diabetes care.
- d. Evaluate the impact of each of the three components of the program (teleconsultations, text messaging and phone calls) on the adherence to basic diabetes self-care behaviors.

2. Activities:

Setting:

Joslin Affiliated Center at Doctor's Hospital at Renaissance in Edinburg (DHR), TX.

Duration:

18 months total:

1. 3 months for IRB approval and training at the partner site
2. 12 months of continuous enrollment (including 9 months of study)
3. 3 months of data analysis and manuscript preparation

Protocol:

Inclusion Criteria:

In order to participate in the program, all patients must meet the following criteria:

1. Have physician-diagnosed type 2 diabetes
2. Be self-identified as Hispanic or Latino
3. Age 21 to 80
4. An A1c value between 8-14% within the last three months.
5. Demonstrate the ability, either alone or with the help of a family member that will be with the patient at least once a week, to use the technology that will be used during the teleconsultations.

Exclusion Criteria:

Subjects will be excluded if they have any of the following conditions:

1. Severe diabetes related chronic complications such as chronic renal failure, blindness, amputations, stroke, etc.
2. Concomitant chronic illnesses that would affect their participation in the program, i.e. cancer, debilitating diseases, etc.
3. Any other condition that would affect participant's basic mental health skills.
4. Type 1 diabetes or gestational diabetes.
5. Patients with abnormal hemoglobin, anemia or any condition that may affect red blood cell turnover. Any of these conditions may be detected through participants' history or through the laboratory report at study screening.
6. Signs or symptoms of metabolic decompensation (polyuria, polydypsia, polyphagia, unexplained weight loss, blurry vision, lethargy, etc.)

Elimination Criteria:

Development of any acute event during the study period that would affect participants' primary outcome at the discretion of the investigator, e.g. hyperosmolar coma, acute event of significant hyperglycemia or the use of certain medications like steroids.

Groups:

A total of 92 participants will be randomly assigned to one of the two study groups:

Group 1 – Intervention group – this group will complete activities described above. During scheduled follow-up clinical visits at months 3, 6, and 9, an additional A1c will be obtained. All measurements will be covered through the study grant if the patient does not have a recent laboratory result (2 weeks prior to the study visit) for the following test: A1c, lipid panel, ALT, AST, microalbumin, and chem 6 result.

Group 2 - Control Group –

This group will attend regular visits with their medical and education providers. As in the intervention group, these visits are expected to occur at 3, 6, and 9 months after the first visit. This group corresponds to the usual care that is provided at DHR.

Primary Outcome:

The primary outcome variable will be the change in hemoglobin A1c value from baseline to 6 months.

Sample Size:

We hypothesize that the decline in hemoglobin A1c value between the baseline and the six-month visit will be at least 0.5 percent greater in the intervention group than in the control group.

The sample size and power calculation is based on preliminary results of our study where the study aimed at behavioral change. Assuming a mean reduction of 0.504 (SD= 1.2) in A1c in the intervention group and no change in the control group a sample size of 37 per group will be needed to detect this reduction with 80 % at 5% level of significance (one-sided) using the t-test. Assuming a 20% dropout, 46 study subjects per group (total 92) will be needed.

Recruitment:

Study Protocol

Study candidates will be identified at the partner site (DHR) where this protocol will take place. This will be done by creating flyers, videos, print and web-based ads, and letters to invite patients that attend the practice to join the study and/or by directly inviting patients that regularly attend the practice. Proper informed written consent will be obtained from all individuals prior to participation in the study.

Interventions:

a. Virtual diabetes self-management group

- i. Weekly conversations led by the diabetes educator (30-minute) using teleconsultation to deliver diabetes education and enhance adherence to treatment recommendations. These conversations will occur during the first 12 weeks of the intervention and will consist of the following elements: a) open question as to whether there is a particular item for discussion that the patient would like to address; b) review of blood glucose and physical activity results; c) review of the adherence to the four basic self-care behaviors (meal plan, physical activity, glucose monitoring and medications); d) identification of barriers to adhere to treatment recommendations; and e) provision of specific recommendations to overcome identified barriers. In order to provide diabetes education in a culturally and linguistically oriented manner, particularly to those patients with low health literacy, all participants in the virtual education program will be encouraged to listen to Rosa's or Jose's Story during the first 8 weeks of the intervention. These are audio-novellas developed by the Latino Diabetes Initiative at Joslin Diabetes Center to educate Latino patients with type 2 diabetes using the story telling method in a practical and engaging manner.
- ii. Since the teleconsultations will only last 12 weeks, phone conversations with the diabetes educator will be implemented starting in the 4th month of the program. These will be 15-30 minute conversations and will occur at weeks 14, 15, 16, 17, 19, 21, and 23. The goal of the phone calls is to provide support to the patients and they will follow the same protocol as the weekly conversations described above.
- iii. A weekly text message will be sent to patients during the 6 months of the education program. These messages will focus on assessing and addressing participants' beliefs about common myths and misconceptions in the area of diabetes. The text message will present the myth of the week and request people's participation in responding whether the concept is true or false and will also provide the correct answer to the question presented the prior week.
- iv. Observation period: the third quarter of the intervention (months 6-9) will allow the observation of the residual effect of the virtual education program; therefore no contact or education will be planned for the last 3 months (months 7, 8 & 9). Patients will be followed in their corresponding clinics as usual.

b. In-person diabetes self-management education or control group

- i. Patients in this group will attend their regular clinical and education appointments as offered by the center.

The table below presents the timeline for the interventions discussed above.

	Months								
	1	2	3	4	5	6	7	8	9
Virtual education	4w R/J 4T	4w R/J 4T	4w 4T	4p 4T	2p 4T	1p 4T			

W=weekly teleconsultation

P=Phone conversation

R/J=Rosa or Jose's Story

T=Text message related to a diabetes myths and misconceptions

Study Procedures:

Before randomization, all participants will go through the following steps:

- 1) Eligible patients will have their standard follow-up clinical encounter with their corresponding health care provider.
- 2) Screening visit. At this time, the research assistant or study coordinator will obtain the baseline A1c measured through each site's laboratory and will review inclusion and exclusion criteria with study candidates to assess eligibility for the study. If the patient qualifies for the study, clinicians will not be aware of this at the time of the initial visit, so that this value does not influence their treatment at baseline and the intervention is left as the main explanatory variable.

After the regular clinical visit and the screening visit the eligible participants will be randomized to one of the two groups.

After randomization, participants will go through the following steps:

- 3) All participants in the study will receive a healthy eating handout, pedometer with exercise handout, and pillbox and will be invited to come to the center for an initial 2-hour nutrition and exercise recommendation group session taught by the diabetes educator. The research assistant and/or study coordinator will provide these items and book to patients that want to participate in the group session.
- 4) Participants in the intervention group will receive education and training on how to operate the technology as well as copies of Rosa's or Jose's Story in their preferred language and based on their education needs. A calendar with specific dates and times for their weekly/monthly interaction with the diabetes team will be provided to participants.

Study Protocol

- 5) All study participants will be given a follow-up appointment 3, 6, and 9 months after the baseline visit.

Project related materials:

Patient Education:

At baseline, all patients in the study will have the opportunity to come to the center for initial 2-hour nutrition and exercise recommendation group session. They will receive handouts regarding food, exercise, medication and will emphasize the need to take medications and insulin on time, follow meal plans, be physically active and monitor blood glucose levels as recommended by their health care provider. This information will be available in English and Spanish and will be based on culturally oriented materials for Latino patients with low/medium health literacy.

Resources for Providers:

All providers will receive training and log-in information for the teleconsultation.

The partner site will receive ***Patient Education Handouts*** (in English and Spanish) that providers can use whenever necessary to support changes to treatment plans for study participants. For instance, handouts on how to start and advance insulin therapy will be provided. Information on other pharmacologic interventions will also be available. Providers will have access to the electronic versions of all handouts

Patient Incentives:

Each participant will receive \$35 every time they complete a study visit. Participants will be asked to complete four study visits in a period of nine months.

Study Visits:

Before any study procedure is done, the patient will be asked to read the consent form. A member of the study staff will discuss the study and the study procedures. Additional time from participants' regular clinical appointments will be necessary to collect study related information as follows:

Visit 1: This visit will last 60 minutes and will start by obtaining an A1c value to verify patient's eligibility. After a patient has been enrolled in the study (A1c value between 8-14%) they will be randomly assigned to the control or intervention group (virtual diabetes self-management education program using teleconsultation) and baseline information will be collected. Participants in the intervention group will be trained to use technology related to the teleconsultation, their own glucometer and the pedometer administered by this program.

Visit 2: This visit will last 60 minutes for questionnaires and will be completed 3 months after visit 1. All the tests and questionnaires detailed in table 1 will be administered at this visit.

Visit 3: This visit will last 60 minutes for questionnaires and will be completed 6 months after visit 1. All the tests and questionnaires detailed in table 1 will be administered at this visit.

Study Protocol

Visit 4: This visit will last 60 minutes for questionnaires and will be completed 9 months after visit 1. All the tests and questionnaires detailed in table 1 will be administered at this visit.

Timeline Table for Study Procedures:

Study Variables (both groups)	Baseline Visit	3	6	9
Laboratories				
Blood drawn	x	x	x	x
A1c	x	x	x	x
Lipid profile	x	x	x	x
ALT (from patient record if available)	x	x		x
AST (from patient record if available)	x	x		x
Microalbumin (from patient record if available)	x		x	x
Chem 6 (from patient record if available)	x	x		x
Measurements				
Weight	x	x	x	x
Height	x			
Blood pressure	x	x	x	x
Questionnaires				
Demographic characteristics	x			
Diabetes history	x			
Diabetes treatment plan	x	x	x	x
Adherence to prescribed drugs	x	x	x	x
Measures of emotional distress (depression, anxiety and PAID)	x		x	
Health literacy	x			
Self-care behaviors	x	x	x	x
Executive function	x			
Depression scale	x	x	x	x
Physical activity: pedometer use and number of steps per day	x	x	x	x
24 hour recall	x	x	x	x
Food frequency questionnaire	x	x	x	x
Analysis of the photo of the content of the refrigerator (only for the intervention group)	x	x	x	x

IRB:

The Joslin Diabetes Center's Institutional Review Board will be in charge of approving this protocol according to current clinical research guidelines.

Study Protocol

An informed consent for participation in the study will be generated to be approved by the IRB. This consent form will be given to all participants before the study begins. Only participants that have given full written consent will be able to participate in the study.

Adverse Events:

We don't anticipate any serious adverse events as this is a study that does not involve the use of any major procedure or the use of any pharmacologic intervention. The only potential adverse events are those related with answering questionnaires or drawing blood for the A1c test and other laboratories specified above.

Good Clinical Practice:

Whereas the primary objective of the protocol is to assess whether there is a significant difference in glycemic control with teleconsultations with the diabetes team at the patient's home, all participants in the study regardless of the **assigned study** group will be offered the best possible diabetes care according to current standards and approved treatment algorithms, particularly the recently published American Diabetes Association standards.

If at any point in time during the study, the investigators or practicing clinicians consider that it would be in the patient's best interest to terminate their participation in the study; this will be considered a priority.

Process and product study variables:

Primary outcome:

- **A1c levels:**

The values obtained through the laboratory at each of the participating sites will be used to evaluate the primary outcome of the study. The baseline A1c value will be used for eligibility for the study.

Other variables:

- **Demographic characteristics** (obtained at baseline)

The demographic variables of interest are: date of birth, years in the practice, household status (living with one or more persons, living alone), years of education, socioeconomic status, community of residence and insurance status.

- **Diabetes history** (obtained at baseline)

The variables of interest are: date of diagnosis, age at diagnosis, years with diabetes, family history of diabetes, diabetes specialist care and history of diabetes education.

- **Diabetes treatment plan** (obtained at baseline and during each clinical encounter in both groups and during the teleconsultations and telephone communications in the intervention group)

- Current meal and exercise plan
- Diabetes treatment (oral medications, injected medication, insulin)

Study Protocol

- Glucose monitoring patterns (number of self-measured blood glucose (SMBG) per day and per week), use of logbook, barriers to SMBG, pre- and post-prandial glucose values.

- **General Medical Evaluation** (obtained at baseline and at every visit)

This evaluation will include: weight and height to calculate body mass index (BMI), waist circumference, blood pressure, capillary glucose level, A1c, smoking habits, aspirin therapy, last eye exam, last microalbumin test, last appointment with an educator, last dental exam and other co-morbidities affecting A1c results.

Lipid Profile: practice will be encouraged to measure lipid profile throughout the study.

- **Adherence to prescribed drugs:**

Medication adherence will be measured through the use of a validated questionnaire called the Morisky Scale.

- **Measures of emotional distress** (will be completed at baseline and last visit)

The Problem Areas in Diabetes (PAID) scale is a well-used and validated tool for measuring diabetes-related distress. The questionnaire has statistically significant power to predict diabetes control in long-term studies. More importantly, the self-reporting tool has been used to study people living with type 2 diabetes in the Latino community. Welch et al. reported a Cronbach's alpha coefficient of .95 in a study evaluating its usefulness in clinical settings. (9)

- **Health literacy:** (will be assessed at baseline)

Each of the participants will be assessed using the Newest Vital Sign (NVS) instrument. (10)

- **Self-care behaviors:** (will be completed at every visit)

We will use the Self-Care Inventory-Revised to measure behavioral changes among patients. This 19-question validated scale measures the subject's perception of the frequency of diabetes-specific tasks performed over the past 1-2 months, such as blood testing, exercising, adherence to medication, and healthy eating. Research supports reliability of the scale in people living with type 2 diabetes. Also, the scale supports an inverse relationship between glycemic control and the mean score of the SCI-R. Weinger et al. reported a Cronbach's alpha coefficient of .87. (11)

- **Depression scale** (will be completed at baseline and 6-month visit)

We will use the Patient Health Questionnaire-9 (PHQ-9). This measure has nine items, each of which is scored, providing a 0 to 27 severity score.

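### Objective c names emergency visits and hospitalisations, but no collection of either is described; objective d's separate component effects rest on strong unstated assumptions; PAID has two conflicting schedules

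*Combined protocol and SAP*

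**What the plan says.** **Objective c** names five outcomes: clinic appointments kept, diabetes-related stress, depression, and "visits to the emergency room and hospitalizations with the use of this program in comparison to people receiving usual diabetes care".

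**Objective d** is to "Evaluate the impact of each of the three components of the program (teleconsultations, text messaging and phone calls) on the adherence" to basic self-care behaviours. The Interventions section lists four such behaviours: meal plan, physical activity, glucose monitoring and medications.

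**Groups:** 92 participants, two arms, whole program or usual care.

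**Component schedule (Interventions, a):**
- Teleconsultations: "These conversations will occur during the first 12 weeks of the intervention".
- Calls: they "will occur at weeks 14, 15, 16, 17, 19, 21, and 23", and follow the same protocol as the teleconsultations.
- Texts: "A weekly text message will be sent to patients during the 6 months of the education program".
- Audio stories, in the first 8 weeks: "all participants in the virtual education program will be encouraged to listen to" them.
- Months 7 to 9: no contact. This period "will allow the observation of the residual effect of the virtual education program".

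**Events:** The Elimination Criteria cover "Development of any acute event during the study period that would affect" the primary outcome, with hyperosmolar coma as one example. The Adverse Events section limits potential events to those arising from questionnaires and blood draws.

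**PAID:** baseline and month 6 in the Timeline Table for Study Procedures; baseline and last visit in the variable list.

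**The concern.** An outcome that is named as a between-arm comparison needs a source, a definition and a time window in both arms. Emergency visits and hospitalisations have none of these. If they are reconstructed after the study, recall will be poorer and may differ by arm, because only the intervention arm has 12 + 7 = 19 educator contacts at which such events might be mentioned.

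Objective d asks a two-arm, whole-package design for three separate effects. Every teleconsultation and every call falls in the period of weekly texts, and no analysis for this objective is described. A published effect of, say, text messaging alone would be a product of modelling assumptions, not of the randomisation.

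The PAID conflict is minor but decides what the score means: month 6 closes the program, and month 9 follows three months without contact.

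**Working it through.** The plan gives no numerical figure for objectives c or d. The only related figure to reproduce is the monthly call count, in step 2.

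**1. Objective c against the collection plan** (Timeline Table; Process and product study variables)

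| Outcome | Collection described |
|---|---|
| Emergency visits | None |
| Hospitalisations | None |
| Appointments | Partial: attendance at months 3, 6 and 9 is knowable from the appointments given to all participants (Study Procedures, step 5) and the visits completed. Beyond that there is only the last educator appointment (General Medical Evaluation) |
| Stress (PAID) | Yes, with conflicting timing |
| Depression (PHQ-9) | Yes; month 6 in both the table and the variable list |

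The Elimination Criteria describe no record of a related emergency visit or admission.

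**2. The week grid.** The interventions table shows 4, 2 and 1 calls in months 4, 5 and 6. Calls in weeks 14, 15, 16, 17, 19, 21 and 23 fall 3/2/2 in 4-week months, and 4/2/1 in months of 26/6 = 4.33 weeks. So 26 weeks fits the table. However, the table's 4 texts × 6 months = 24 texts, so both grids are carried below.

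**3. Once-per-visit measures** (SCI-R, which looks back 1-2 months, and the medication-adherence questionnaire). Let T, X and P be the effects of teleconsultation, text and phone, and c a carryover common to all three. The between-arm differences are:
- month 3: T + X
- month 6: c(T + X) + X + P
- month 9: c × (month 6)

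Month 9 only rescales month 6, so the rank is 2 for 3 unknowns at c = 0, 0.25, 0.5, 0.75 and 1. Replacing (T, X, P) by (T + k, X − k, P + k) leaves all three differences unchanged. Only T + X, X + P and T − P are estimable. The T + X contrast also contains the audio stories.

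**4. Week-level device data.** Fitbit and meter data are downloaded in both arms and cover physical activity and glucose monitoring, two of the four behaviours. If texts are weekly:

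| Weeks with | 24-week grid | 26-week grid |
|---|---|---|
| Teleconsultation + text | 12 | 12 |
| Phone + text | 7 | 7 |
| Text only | 5 (13, 18, 20, 22, 24) | 7 (also 25, 26) |

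With additive, time-constant effects the rank is 3 of 3. With no carryover, X is the text-only mean, P is the call-week mean minus X, and T is the weeks 1-12 mean minus X.

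*Text effect allowed to differ by phase.* No text-only week precedes week 13. Split X into weeks 1-12 and later: the early-text column is then identical to the teleconsultation column. The rank is 3 of 4 on either grid, for weekly carryover of 0, 0.25, 0.5, 0.75 or 0.9. T is not estimable, only T + X(early).

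*Carryover ignored.* Let the truth be a call effect of 1, with half persisting each following week, and T = X = 0. The mean over the 7 call weeks is 1.472. The text-only weeks 13, 18, 20, 22 and 24 hold 0, 0.938, 0.734, 0.684 and 0.671; weeks 25 and 26 hold 0.335 and 0.168.
- 24 weeks: X = 3.026/5 = +0.61; P = 1.472 − 0.605 = 0.87; T = 0 − 0.605 = −0.61.
- 26 weeks: X = 3.530/7 = +0.50; P = 1.472 − 0.504 = 0.97; T = −0.50.

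Two inert components appear active.

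**5. What event data could show.** The documents give no event rates. Assume that a control-arm proportion of 10%, 20%, 30% or 40% is halved, with the plan's 37 completers per arm (Fisher exact test, two-sided 5%). Power is 3.5%, 14.2%, 25.3% or 38.2%. The data would be descriptive.

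**6. PAID and PHQ-9.** PAID follow-up is month 6 in the table and month 9 (Visit 4) in the variable list. The table's depression-scale row marks every visit, while the variable list gives baseline and month 6.

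**The case against.** Several points on the other side are sound and limit the conclusion.

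- *Appointments.* A reader might infer that nothing shows whether appointments were kept. The documents do not support that: all participants get appointments at 3, 6 and 9 months, and payment is made for each completed visit. What remains uncaptured is other clinic and education appointments.
- *Identifiability.* A reader might infer that the components can never be separated, or only if carryover is known in advance. Neither holds. Under an additive model with one geometric carryover, weekly data can estimate the carryover as a fourth unknown (Jacobian rank 4 of 4 at 0.25, 0.5, 0.75 and 0.9, with illustrative effects). At visit level, differing carryovers assumed known (for example 0.5, 0.25 and 0.4 for T, X and P) give rank 3. But separation then rests on the assumed values or model, and the plan states neither.
- *Text-free weeks.* Months 7-9 have no texts, and 24 texts over 26 weeks could leave two more text-free weeks. Months 7-9 supply no text-only week during weeks 1-12, and where any other gap would fall is not stated.
- *Framing.* Unlike objectives a and c, objective d does not mention usual care, so a within-arm analysis may be intended. That loses the randomised comparison and keeps the same overlap of components.
- *PAID.* The descriptions of Visits 2 to 4 say that all listed tests and questionnaires are given, which might suggest a third schedule. Read that way, baseline-only items such as demographics and health literacy would also be repeated. The natural reading is that items are given as marked, which leaves two versions.

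**Conclusion.** The point holds, and the sponsor should act on it. Its weight lies in objective c: two of five named outcomes have no collection described, and a third is partial. That finding needs no modelling assumption.

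For objective d, the plan does not credibly support an effect of any single component. The visit-level result (rank 2 for 3) assumes a common carryover. The week-level result covers two of four behaviours, and the teleconsultation effect depends wholly on texts working the same in weeks 1-12 as later. The counts of 5 or 7 text-only weeks assume weekly texts over 24 or 26 weeks.

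The PAID conflict is minor. PHQ-9 timing also differs, but month 6 is in both versions. A reader might infer that these gaps threaten the trial's main result. They do not: A1c at baseline and month 6 is collected in both arms.

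**What to change.** 1. Add emergency visits, hospitalisations, and appointments kept and missed since the last visit to the 3-, 6- and 9-month forms. Ask identically in both arms at the study visit, not through the educator contacts. Include any event that led to elimination, and report descriptively. Otherwise remove emergency visits and hospitalisations from objective c.
2. Reword objective d. Report the between-arm difference at month 3 (teleconsultations, texts and audio stories) and at month 6 (whole program, including whatever persists from months 1-3). Add logged engagement with each component (teleconsultations and calls completed, texts answered) and its association with adherence within the intervention arm. Make no causal claim for a single component.
3. Label any week-level device analysis exploratory, state its assumptions and vary the carryover.
4. Reconcile the PAID and PHQ-9 schedules so that both include month 6 in both arms.

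The cost is slightly longer forms at visits already scheduled, a simple contact log and a more modest objective d.

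### Discretionary post-randomisation elimination for events that affect A1c selects on the primary outcome and can bias the comparison in either direction

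*Combined protocol and SAP*

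**What the plan says.** The Elimination Criteria section stands apart from the exclusion criteria and applies after enrolment. Its trigger is "Development of any acute event during the study period that would affect participants' primary outcome at the discretion of the investigator", with the examples "hyperosmolar coma, acute event of significant hyperglycemia or the use of certain medications like steroids". The primary outcome, stated under that heading, is the A1c change from baseline to 6 months.

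The consequence of elimination is not defined. The document gives no intention-to-treat or other analysis set, no method for missing data, no glucose threshold, no masked adjudication and no deadline for the decision. The one concealment statement, under Study Procedures, concerns clinicians' knowledge of eligibility at the initial visit.

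Three other places bear on the point:

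- **Sample Size:** "Assuming a 20% dropout, 46 study subjects per group (total 92) will be needed". It does not say whether eliminations count within the 20%.
- **Good Clinical Practice:** a separate clause gives priority to ending participation when investigators or clinicians judge that "it would be in the patient's best interest to terminate their participation in the study". It neither limits nor explains the elimination rule.
- **Timeline Table for Study Procedures:** A1c is scheduled at baseline and at 3, 6 and 9 months in both groups.

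**The concern.** Randomisation protects the comparison only if the groups analysed are the groups randomised. Here removal depends on something that happens after randomisation and is defined by its effect on the outcome. Hyperosmolar coma and significant hyperglycaemia are failures of the control the program is meant to improve. Steroid use is not a measure of glycaemic control, but it too arises after randomisation.

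Bias can arise in two ways.

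- **Unequal detection or judgement.** Both arms have A1c and meter downloads at study visits. The intervention arm alone has weekly teleconsultations that review glucose ("These conversations will occur during the first 12 weeks of the intervention"), then seven calls on the same protocol ("15-30 minute conversations and will occur at weeks 14, 15, 16, 17, 19, 21, and 23"), treatment and glucose data gathered at those contacts, and optional home meter syncing. No masking after randomisation is described, so the investigator presumably knows the group. If more events come to light in the intervention arm, more of its poor responders are removed and the program looks better than it is.
- **A program that works.** If the program prevents hyperglycaemic events, an impartial rule removes more controls, and the benefit is understated.

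The study period runs to 9 months, so nothing written prevents an elimination decision after the 6-month A1c is known. Elimination could also discard emergency visits and hospitalisations that objective c sets out to compare.

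**Working it through.** **Inputs.** From Sample Size: target difference 0.504, SD 1.2, 37 analysed per group, one-sided 5% t-test, 20% dropout, 46 per group. Elimination rates and cut-offs are assumptions, because the document gives none. D is the mean A1c change in controls minus that in the intervention arm, so positive D favours the program.

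**The plan's own figures.** 37/0.80 = 46.25, stated as 46; 46 × 0.80 = 36.8. The 37 itself is a one-sample or paired figure: ((1.645 + 0.842) × 1.2/0.504)² = 35.0, or 36.4 with the t-distribution, hence 37. A two-group t-test needs 71 per group. That is a separate matter; 37 is used below only as the plan's analysed number.

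**1. Simple scale.** If a fraction f of an arm is removed and those removed average d above the rest, the arm mean moves by f × d. For 3 of 37 with d = 2.0: (3/37) × 2.0 = 0.162, and 0.162/0.504 = 32% of the target effect.

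**2. No true effect.** Those removed are drawn from participants whose change exceeds 1.2 (one SD). Their mean is 1.2 × φ(1)/(1 − Φ(1)) = 1.83. Removing a fraction f lowers the arm mean by f × 1.83/(1 − f):

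- f = 5%: 0.05 × 1.83/0.95 = 0.096
- f = 2.5%: 0.025 × 1.83/0.975 = 0.047

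Type I error is from 40,000 simulated trials, 37 per arm, pooled one-sided t-test at 5%:

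| Removed, intervention / control | Shift in D | Type I error |
|---|---|---|
| none | 0 | 4.8% |
| 5% / 0% | +0.10 | 9.6% |
| 5% / 2.5% | +0.05 | 7.2% |
| 5% / 5% | 0 | 5.1% |
| 0% / 5% | −0.10 | 2.4% |

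**3. True effect 0.504, one neutral cut-off c in both arms.** The mean of those kept is μ − 1.2 × φ(a)/Φ(a), with a = (c − μ)/1.2; μ = 0 for controls and −0.504 for the intervention arm.

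| c | Removed, control / intervention | Mean kept, control | Mean kept, intervention | D |
|---|---|---|---|---|
| 2.46 | 2.0% / 0.7% | −0.059 | −0.527 | 0.467 |
| 1.97 | 5.0% / 1.9% | −0.130 | −0.562 | 0.432 |
| 1.54 | 10.0% / 4.4% | −0.234 | −0.622 | 0.388 |

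A softer neutral rule gives anyone rising by more than 1.2 the same 31.5% chance of elimination. It removes 5.0% of controls and 2.5% of the intervention arm. The means kept are −0.096 and −0.560, so D = 0.464.

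**4. Wider assumptions.** Suppose there is no true effect, every intervention participant above the cut-off is eliminated, and half of such controls are. Cut-offs of 2.0, 1.5 and 1.0 then give spurious benefits of 0.06, 0.13 and 0.24, with type I error 7.8%, 12.3% and 22.5%. The last case removes 20.2% and 10.1% of the arms, which is heavy.

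**5. Numbers left.** If eliminations of 5% came on top of the 20% dropout, 46 × 0.75 = 34.5 per group would remain, against 36.8.

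**The case against.** The protocol never says that eliminated participants leave the analysis or that their A1c goes uncollected. If elimination only stops study activities while A1c is still measured and analysed, none of this bias arises. That is correct: what is certain is the gap in the text, and the bias depends on the natural reading.

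The illustrations also remove people directly on their own 6-month A1c change. The protocol's trigger is an acute event or a medication, and an event in month 1 need not mean a large rise at month 6. The figures therefore lean towards the upper end for a given removal rate, and the 9.6% needs removals in one arm only. With equal removal and no true effect there is no mean bias. Where judgement and detection are neutral and the program works, the error is conservative.

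Unequal detection is inferred, not shown. The General Medical Evaluation at every visit covers co-morbidities affecting A1c and is not limited to one arm, a coma would hardly be found only through an educator's call, and home syncing is optional. Baseline and 3-month A1c could support an analysis when the 6-month value is missing, but only under assumptions about the missing value. A 20% allowance can fairly be read as covering all losses, so the 34.5 carries little weight.

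These points limit how large and how certain the bias is. They do not supply the missing analysis set, continued follow-up or masked judgement.

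**Conclusion.** The concern holds and must be fixed before analysis. The protocol contains an active, discretionary rule for removing randomised participants, defined by effect on the primary outcome, and nothing elsewhere contains its consequences. Followed on its natural reading, it breaks the randomised comparison.

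The direction cannot be known in advance. In the main illustrations, 5% removed from one arm only moves the difference by about 0.10 either way, with type I error between 2.4% and 9.6% against a nominal 5%. A neutral rule with a working program cuts 0.504 to between 0.47 and 0.39 when 2% to 10% of controls are removed. These figures assume normally distributed changes with SD 1.2, 37 analysed per arm and removal tied closely to the A1c change. They show scale and do not predict what this trial will see. A 6-month A1c that is never collected can later be replaced only under untestable assumptions.

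**What to change.** Amend the Elimination Criteria section and add an analysis-set statement:

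- The listed events do not remove a participant from study follow-up or from the analysis.
- Where the participant remains willing, the A1c already scheduled at 3, 6 and 9 months is still collected. Treatment and the best-interest clause under Good Clinical Practice are unchanged.
- All randomised participants are analysed in their assigned group.
- Each event is recorded with its date, and the number of events is reported by arm.
- Excluding affected A1c values is a sensitivity analysis only, with events classified by prespecified criteria and without knowledge of group or A1c result.
- Sample Size states whether losses of this kind fall within the 20% allowance.

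The cost is mainly wording, since the A1c measurements are already planned for both groups. The funding statement, "All measurements will be covered through the study grant if the patient does not have a recent laboratory result", appears only under Group 1, so coverage for controls should be confirmed. The statistical price is that a few A1c values affected by acute events or steroids add some noise to the primary analysis.
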